## **6.7. Intervention after the End of the Study**

Tirzepatide will not be made available to participants after conclusion of the study.

## 7. Discontinuation of Study Intervention and Participant Discontinuation/Withdrawal

### 7.1. Discontinuation of Study Intervention

In rare instances, it may be necessary for a participant to permanently discontinue (definitive discontinuation) study drug intervention. If intervention is definitively discontinued, the participant will remain in the study to be evaluated for any trial endpoint at the end of the study. See the SoA for data to be collected at the time of discontinuation of study drug intervention and follow-up and for any further evaluations that need to be completed.

In some instances, it may be necessary for a participant to permanently discontinue the intensive lifestyle intervention during the 12-week lead-in phase. If the intensive lifestyle intervention is discontinued during the lead-in period, the participant will be permanently discontinued from the study.

#### **Possible reasons leading to permanent discontinuation of intensive lifestyle intervention during lead-in period or study drug intervention during treatment period:**

- **Participant Decision**
  - The participant requests to discontinue intensive lifestyle intervention during the lead-in period or study drug intervention during treatment period.
  
- **Clinical Considerations**
  - Initiation of open-label GLP-1R agonist or DPP-4 inhibitor, if participants will not or cannot discontinue them
  - BMI  $\leq 18.5$  kg/m^2 is reached at any time
    - Note:* The investigator should contact the sponsor CRP to discuss whether it is medically appropriate for the participant to continue study treatment
  - Diagnosis of T1DM
  - Diagnosis of MTC or MEN syndrome type 2
  - Significant elevation of serum calcitonin (Section 8.3.2.4)
  - Diagnosis of acute or chronic pancreatitis
  - Diagnosis of an active or untreated malignancy (other than basal or squamous cell skin cancer, in situ carcinomas of the cervix, or in situ prostate cancer)
  - Onset of pregnancy in a female participant
  - Occurrence of any other treatment-emergent AE (TEAE), SAE, or clinically significant finding for which the investigator believes that permanent discontinuation is the appropriate measure to be taken
  - Inadvertent enrollment if continued intensive lifestyle intervention or treatment with study drug would not be medically appropriate or not allowed per local regulations
  - PHQ-9 score  $\geq 15$ .

- Participants should be referred to a Mental Health Professional (MHP) to assist in deciding whether the participant should be discontinued. If a participant's psychiatric disorder can be adequately treated with psycho- and/or pharmacotherapy, then the participant, at the discretion of the investigator (in agreement with the MHP), may be continued in the trial.
  - Participants with C-SSRS responses **at any visit** indicative of suicidal ideation or behavior should have intensive lifestyle or study drug interventions discontinued and be referred to an MHP. Both interventions may be restarted, if the MHP and the investigator agree it is appropriate for the participant. Responses that should prompt mental health referral and cessation of intensive lifestyle intervention or study drug intervention are
    - a “yes” answer to Question 4 (Active Suicidal Ideation with Some Intent to Act, Without Specific Plan) on the "Suicidal Ideation" portion of the C-SSRS
    - or**
    - a “yes” answer to Question 5 (Active Suicidal Ideation with Specific Plan and Intent) on the "Suicidal Ideation" portion of the C-SSRS
    - or**
    - a “yes” answer to any of the suicide-related behaviors (actual attempt, interrupted attempt, aborted attempt, preparatory act or behavior) on the “Suicidal Behavior” portion of the C-SSRS

*Note:* A psychiatrist or appropriately trained professional may assist in the decision to discontinue the participant.

- **Discontinuation due to a hepatic event or liver test abnormality.**
  - Participants who are discontinued from intensive lifestyle intervention or study drug intervention due to a hepatic event or liver test abnormality should have additional hepatic safety data collected via eCRF.
  - Discontinuation of intensive lifestyle intervention or study drug intervention for abnormal liver tests **should be** considered by the investigator when a participant meets one of the following conditions after consultation with the Lilly designated medical monitor:
    - ALT or aspartate aminotransferase (AST) >8X ULN
    - ALT >2X baseline value or  $\geq 300$  U/L, whichever occurs first, if baseline ALT  $\geq 2$ X ULN
    - ALT or AST >5X ULN for more than 2 weeks
    - ALT or AST >3X ULN and TBL >2X ULN or international normalized ratio (INR) >1.5
    - ALT or AST >3X ULN with the appearance of fatigue, nausea, vomiting, right upper-quadrant pain or tenderness, fever, rash, and/or eosinophilia (>5%)

- ALP >3X ULN
- ALP >2.5X ULN and TBL >2X ULN
- ALP >2.5X ULN with the appearance of fatigue, nausea, vomiting, right upper-quadrant pain or tenderness, fever, rash, and/or eosinophilia (>5%)

*Note:* In this study baseline may refer to lead-in enrollment visits or randomization visit, whichever is the most recent point of reference.

**The following are also applicable if developing/occurring during intensive lifestyle lead-in period:**

- Ketoacidosis or hyperosmolar state/coma
- Uncontrolled hypertension (systolic blood pressure above or equal to 160 mmHg and/or diastolic blood pressure above or equal to 100 mmHg)
- Diagnosis of any of the following cardiovascular conditions:
  - Acute myocardial infarction
  - Cerebrovascular accident (stroke)
  - Unstable angina
  - Hospitalization due to CHF, or
  - NYHA Functional Classification Class IV CHF
- Chronic (>2 weeks or >14 days) systemic glucocorticoid therapy (excluding topical, intra-ocular, intranasal, intra-articular, or inhaled preparations) or evidence of a significant, active autoimmune abnormality (for example, lupus or rheumatoid arthritis) that has required or is likely to require, in the opinion of the investigator, concurrent treatment with systemic glucocorticoids (excluding the ones mentioned above)
- Surgical treatment or endoscopic and/or device-based therapy for obesity
- Initiation of treatment with medications that may significantly impact body weight (please refer to Section 5.2. for details)
- Initiation of implantable or injectable contraceptives (such as Depo Provera®)

**The following are also applicable during study drug intervention period (after randomization):**

- Intolerable GI symptoms despite management as described in Section 6.6.2
- If the investigator, after consultation with the sponsor-designated medical monitor, determines that a systemic hypersensitivity reaction has occurred related to study drug administration, the participant should be permanently discontinued from the investigational drug.

Participants who stop intensive lifestyle intervention permanently should perform an early discontinuation (ED) visit and discontinue from the study. Participants who stop the study drug permanently should perform an ED visit and continue to attend all scheduled study visits to collect all planned efficacy and safety measurements. Randomized participants who are unwilling to attend all scheduled visits and stop the study treatment prior to 72 weeks, should

return for a final weight measurement (Visit 99). If participants are unwilling to attend Visit 99, their refusal to attend should be documented in the patient medical record.

See the SoA for data to be collected at the time of intervention discontinuation and follow-up and for any further evaluations that need to be completed.

### 7.1.1. Temporary Discontinuation

In certain situations, after randomization, the investigator may need to temporarily interrupt study drug. Every effort should be made by the investigator to maintain participants on study drug and to restart study drug after any temporary interruption, as soon as it is safe to do so. Distribution of study drug at the correct dose will be per IWRS instructions.

If study drug interruption is...	then...
2 consecutive doses or less	participant restarts study drug at last administered dose, as per escalation schedule.
3 consecutive doses or more	participant restarts study drug at 5 mg (managed by IWRS) and repeats dose escalation scheme.
due to an AE	the event is to be documented and followed according to the procedures in Section 8.3 of this protocol.
due to intolerable persistent GI AE	participants should be treated as suggested in Section 6.6.2.

Investigators should inform the sponsor that study drug has been temporarily interrupted. The data related to temporary interruption of study treatment will be documented in source documents and entered on the eCRF.

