### ***End of Visit 10 to Visit 28***

During the treatment period, office visits will occur as indicated in the SoA (Section 1.3). Telephone visits will occur at 4-week intervals between the office visits starting at Visit 17.

Office visit procedures should be conducted according to the SoA (Section 1.3), and will include

- weight, waist circumference and vital signs measurements
- laboratory testing
- administration of PRO questionnaires
- collection of AEs, product complaints and concomitant medications
- Mental Health questionnaires
- review of participant diary information (to include reinforcement and compliance assessments for study drug administration and lifestyle goals)
- drug dispensing.

Patient-reported outcomes questionnaires should be administered as early as possible, as per Suggested Visit Structure (Section 10.8). Preferred administration order is the same as Visit 2.

Mental Health questionnaires should be completed after the assessment of AEs.

Dietician consultations occur every 12 weeks from Week 0 to Week 72. Study drug and injection supplies will be returned per the SoA (Section 1.3) and according to local requirements. New supplies will be dispensed as needed.

The starting dose of tirzepatide is 2.5 mg QW (or matching placebo) for 4 weeks, then the dose is increased by 2.5 mg (or matching placebo) every 4 weeks (2.5 to 5 to 7.5 to 10 to 12.5 to 15 mg) up to MTD (either 10 mg or 15 mg).

Interventions to optimize study drug tolerance and adherence may be employed throughout the study and include, but are not limited to, brief temporary interruptions and use of additional medications to manage GI symptoms (for example, nausea, vomiting, and diarrhea, see Section 6.6.2. for details).

During the first 24 weeks of the treatment period (20-week dose escalation plus 4 weeks), participants unable to tolerate 2.5 mg or 5 mg despite the above measures will be discontinued from the study drug but remain in the study for continued follow up. For participants unable to tolerate any dose escalation between 7.5 mg and 15 mg inclusive, despite the above measures, the investigator should contact Lilly to consider a dose de-escalation step with subsequent re-escalation in a blinded fashion to reach either the 10-mg or 15-mg dose as described below (only 1 cycle of dose de-escalation and re-escalation is permitted during the first 24 weeks of the treatment period):

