### **4.3. Justification for Dose**

Tirzepatide MTD (10 mg or 15 mg QW) will be evaluated in this study. These doses and associated escalation schemes were selected based on assessment of safety, efficacy (weight loss), and GI tolerability data in Phase 1 and 2 studies in patients with T2DM, followed by exposure-response modeling of the data that predicted weight loss in patients with overweight or obesity.

In a 26-week, Phase 2 study (GPGB) of participants with T2DM, tirzepatide reduced body weight by 4.8 kg, 8.7 kg, and 11.3 kg at dose levels of 5, 10, and 15 mg, respectively, whereas the weight loss observed in participants on dulaglutide, a selective GLP-1R agonist, used at the dose of 1.5 mg, was 2.7 kg (Frias et al. 2018).

Similar to the GLP-1R agonist class, most of the tirzepatide AEs were dose-dependent and GI-related, consisting mainly of nausea, vomiting, and diarrhea. In general, these events were mild or moderate in severity, with few severe episodes, and transient.

Tirzepatide doses of 10 mg and 15 mg were selected based principally on the following criteria:

- each dose provides robust weight loss relative to placebo
- the percent of patients achieving  $\geq 10\%$  weight loss is higher with 15 mg than 10 mg, and
- safety and tolerability were supported by Phase 2 results and/or PK/PD modeling.

Dosing algorithms starting at a low dose of 2.5 mg accompanied by dose escalation of 2.5-mg increments every 4 weeks should permit time for development of tolerance to GI events and are predicted to minimize GI tolerability concerns. The maximum proposed dose of 15 mg maintains an exposure multiple of 1.6 to 2.4 to the no-observed adverse effect level doses in 6-month monkey and rat toxicology studies.

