### 6.1. Study Intervention(s) Administered

Arm Name	Tirzepatide MTD	Placebo
Dose	10 mg or 15 mg QW	N/A
Route of Administration	SC	
Sourcing	Provided centrally by the sponsor and dispensed via IWRS	
Packaging and Labeling	Study drug intervention will be provided in autoinjectors (single-dose pens) packaged in cartons to be dispensed. Clinical study materials will be labeled according to country regulatory requirements.	

Abbreviations: IWRS = interactive web-response system; MTD = maximum tolerated dose; N/A = not applicable; QW = once-weekly; SC = subcutaneous.

There are no restrictions on the time of day each weekly dose of study drug is given, but it is advisable to administer the SC injections on the same day and same time each week. The actual date, time, and injection site location of all dose administrations will be recorded in the diary by the participant. If a dose of study drug is missed, the participant should take it as soon as possible unless it is within 72 hours of the next dose, in which case, that dose should be skipped and the next dose should be taken at the appropriate time. The day of weekly administration can be changed if necessary, as long as the last dose was administered 72 or more hours before.

All participants will inject study drug SC in the abdomen or thigh using the injection supplies provided; a caregiver may administer the injection in the participant's upper arm. The injection-site location of all dose administrations will be recorded in the diary by the participant. A new autoinjector will be used for each injection. If study drug is to always be injected in the same body region, participants should be advised to rotate injection sites each week.

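### Section 7.1.1 restarts participants at 5 mg after three or more missed doses, even if they have taken only one to three of the four planned 2.5 mg doses

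*Protocol*

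**What the plan says.** Section 7.1.1 of the protocol covers temporary interruption of study drug at any time after randomization. For three or more consecutive missed doses, its table says "participant restarts study drug at 5 mg (managed by IWRS) and repeats dose escalation scheme". The dose already reached plays no part in that row. For two or fewer missed doses the row reads "participant restarts study drug at last administered dose, as per escalation schedule".

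Section 4.1.1.2.3 sets the planned escalation: "The starting dose of tirzepatide is 2.5 mg QW (or matching placebo) for 4 weeks", then increases of 2.5 mg every four weeks up to 15 mg. Section 4.3 gives the reason: a low start with 2.5 mg increments "every 4 weeks should permit time for development of tolerance to GI events".

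Three other rules bear on the case:

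- The de-escalation ladder in Section 4.1.1.2.3 has 7.5 mg to 5 mg as its lowest step. Below that, "participants unable to tolerate 2.5 mg or 5 mg despite the above measures will be discontinued from the study drug".
- Section 6.6.1 allows dose modification only for intolerable GI symptoms, from Week 0 to Week 24.
- Section 6.6.2 sends interruptions of more than one dose back to Section 7.1.1.

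SAP Section 6.2 plans to summarize dose interruptions if the data warrant, but gives no restart rule.

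**The concern.** The 5 mg restart looks designed for participants who are already at or above 5 mg, for whom it holds or lowers the dose. Applied to a participant who has not finished the 2.5 mg step, it cuts that step short, and the protocol gives no reason for doing so. No other section returns this participant to 2.5 mg. After a non-GI interruption the site has no stated authority to choose 2.5 mg itself.

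What is at stake is early tolerability. These participants meet 5 mg with less 2.5 mg exposure than planned. If they then cannot tolerate 5 mg despite the GI measures, study drug is stopped, because the ladder offers no step down. That stopping rule applies to everyone at 5 mg; the only difference here is the shorter preparation.

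**Working it through.** The plan states no figure on this point, so the check is to apply the Section 7.1.1 row to the Section 4.1.1.2.3 schedule.

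**Schedule.** 2.5 mg in Weeks 0-3, 5 mg in Weeks 4-7, then +2.5 mg every four weeks. From 2.5 to 15 mg is 5 increments × 4 weeks = 20 weeks, which matches the 20-week escalation period stated in Section 4.1. From 5 to 15 mg is 4 × 4 = 16 weeks.

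**Direction of the row.** Restart dose divided by last dose is 5/2.5 = 2.0; 5/5 = 1.0; 5/7.5 = 0.67; 5/10 = 0.5; 5/12.5 = 0.4; 5/15 = 0.33. Only at 2.5 mg does the row raise the dose.

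**Who is affected.** Let k be the doses of 2.5 mg taken and m the consecutive doses missed, with m at least 3.

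- Restart week = k + m.
- 2.5 mg doses skipped = 4 − k, so 3, 2 or 1 for k = 1, 2 or 3.
- At k = 4 the step is complete and 5 mg is the next planned dose, so that case is not part of the point. From the fifth dose on, 5 mg has already been taken.
- The earliest restart is 1 + 3 = Week 4, when 5 mg is already the calendar dose. No participant receives 5 mg ahead of the calendar.

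**Timing of the first 15 mg dose.**

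- Current rule: k + m + 16, that is Week 17 + m to 19 + m.
- Giving only the remaining 2.5 mg doses first: (k + m) + (4 − k) + 16 = Week 20 + m.
- Repeating the whole 2.5 mg step: k + m + 4 + 16 = k + m + 20.

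| Doses missed (m) | Current rule (k = 1, 2, 3) | Remaining doses first | Whole step repeated (k = 1, 2, 3) |
|---|---|---|---|
| 3 | Week 20, 21, 22 | Week 23 | Week 24, 25, 26 |
| 4 | Week 21, 22, 23 | Week 24 | Week 25, 26, 27 |
| 5 | Week 22, 23, 24 | Week 25 | Week 26, 27, 28 |

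**Time left for GI de-escalation at 15 mg.** The window closes at Week 24 (Sections 4.1.1.2.3 and 6.6.2).

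- Three missed doses: 24 − 20, 24 − 21 and 24 − 22 = 4, 3 or 2 weeks now, against 24 − 23 = 1 week with the remaining doses given.
- Four missed doses: 3, 2 or 1 weeks now, against none.

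The current rule already produces the same timing for other participants. Five doses taken and three missed means restart at Week 8 and the first 15 mg dose at 8 + 16 = Week 24.

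**The case against.** The strongest reply is that little is lost. Moving from 2.5 mg to 5 mg is everyone's planned first increase, so the ratio of 2.0 is not an excess. Section 2.2 lists multiple 5 mg weekly doses in patients with type 2 diabetes, with titration mentioned only for 15 mg, and a maximum tolerated single dose of 5 mg in healthy subjects. Many GI cases go elsewhere: Section 6.6.2 permits a one-dose interruption only if the last three weekly doses were taken, and participants who cannot tolerate 2.5 mg stop study drug. Dispensing is managed by the IWRS, whose specification is not among the documents. All of this stands and keeps the point small. It does not close the gap, because Section 6.6.2 returns longer interruptions to Section 7.1.1 and non-GI interruptions have no other route.

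A second objection concerns the remedy: from four missed doses it leaves no de-escalation time at 15 mg before Week 24. That is correct and is a real cost. It is not decisive, since the protocol already accepts that timing for participants who miss three or more doses after starting 5 mg.

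A reader might infer two stronger claims.

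- **A longer interruption earns a higher dose than a shorter one.** This depends on the two-dose row, which is ambiguous. With two or three doses taken and two missed, restart falls at Week 4 or 5. The phrase "participant restarts study drug at last administered dose, as per escalation schedule" could then mean 2.5 mg, the last dose given, or 5 mg, the scheduled dose. The point therefore rests on the three-dose row alone.
- **Participants are exposed to a hazard.** The documents show none, and 5 mg never comes before its calendar week.

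**Conclusion.** The point holds as a minor tolerability gap. As written, Section 7.1.1 skips one to three of the four 2.5 mg doses for participants who interrupt for three or more doses before finishing that step, contrary to the rationale in Section 4.3. The group is confined to interruptions that begin after the first, second or third dose. Its size cannot be estimated, because the documents give no interruption rate.

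Two assumptions carry the conclusion: that the three-dose row is applied literally, and that the IWRS has no separate 2.5 mg branch. If such a branch exists, only the protocol wording needs correcting. Power, alpha, sample size and the planned analyses are unaffected.

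**What to change.** Reword the three-dose row of Section 7.1.1 along these lines: *restart at 5 mg, or at 2.5 mg if 5 mg has never been taken and fewer than four 2.5 mg doses have been given; in that case complete the remaining 2.5 mg doses, then continue the escalation.* Confirm that the IWRS dispenses accordingly.

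The cost is one table row and one logic check, with no added visits or participants. Escalation is one to three weeks slower for the few affected, and the first 15 mg dose moves to Week 20 + m. The sponsor should accept knowingly that this leaves one week for GI de-escalation at 15 mg after three missed doses and none from four. Giving only the remaining doses is better than repeating the whole step, which already reaches Week 24-26 with three missed.

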### 7.2. Participant Discontinuation/Withdrawal from the Study

To minimize the amount of missing data and to enable assessment of study objectives as planned in the study protocol, every attempt will be made to keep participants in the study irrespective of the following:

- adherence to or discontinuation from study drug
- adherence to visit schedule
- missing assessments
- study drug discontinuation due to AE
- development of comorbidities
- development of clinical outcomes

The circumstances listed above are **not** valid reasons for discontinuation from the study.

A participant may withdraw from the study:

- at any time at his/her own request
- at the request of his/her designee (for example, parents or legal guardian)
- at the discretion of the investigator for safety, behavioral, compliance, or administrative reasons
- if enrolled in any other clinical study involving an IP or enrolled in any other type of medical research judged not to be scientifically or medically compatible with this study
- if the participant, for any reason, requires treatment (for example, pharmacological, device-based or surgical) that has been demonstrated to be effective for treatment of the study indication, discontinuation from the study occurs prior to introduction of the new treatment

[figure not shown]
Female participants will be withdrawn from the study if the participant becomes pregnant.

Participation in the study can be stopped for medical, safety, regulatory, or other reasons consistent with applicable laws, regulations, and Good Clinical Practice (GCP). Participants who agree to provide information relevant to any trial endpoint at the end of the study are not considered to have discontinued from the study.

At the time of discontinuing from the study, if possible, an ED visit should be conducted, as shown in the SoA. See the SoA for data to be collected at the time of study discontinuation and follow-up and for any further evaluations that need to be completed. The participant will be permanently discontinued from either the intensive lifestyle intervention or study drug intervention, and from the study at that time.

If the participant withdraws consent for disclosure of future information, the sponsor may retain and continue to use any data collected before such a withdrawal of consent. If a participant withdraws from the study, he/she may request destruction of any samples taken and not tested, and the investigator must document this in the site study records.

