**4.1.1.3. *Safety Follow-Up Period******Visit 801***

All randomized participants are required to complete a safety follow-up visit (Visit 801), according to the SoA. Participants discontinuing the study drug early and performing an ED visit will also be asked to perform the safety follow-up visit (see Section 7.2). During the safety follow-up period, participants will not receive study drug. Participants are also required to return any remaining study diaries to the study site at the end of this period.

Visit 801 (safety follow-up visit) should be performed 4 weeks after the last visit in the treatment period (Visit 28 or Visit 99) or 4 weeks after the ED visit for randomized participants who decline to return for Visit 99.

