## 6.3. Measures to Minimize Bias: Randomization and Blinding

This is a double-blind, randomized study.

Participants who meet all criteria for enrollment will undergo a 12-week intensive lifestyle modification lead-in period. Those who achieve  $\geq 5.0\%$  weight loss at Visit 10 will be randomized to one of the study treatment groups (tirzepatide MTD or placebo) for the duration of the treatment period. Assignment to treatment groups will be determined by a computer-generated random sequence using an IWRS. Participants will be randomized in a 1:1 ratio to receive tirzepatide MTD or placebo.

The randomization will be stratified by country, sex (female, male), and percent weight loss at the end of lead-in ( $<10\%$  versus  $\geq 10\%$ ).

Investigators, site staff, clinical monitors and participants will remain blinded to the treatment assignments until the study is complete.

Emergency unblinding for AEs may be performed through the IWRS. This option may be used ONLY if the participant's well-being requires knowledge of the participant's treatment assignment. All emergency unblinding events are recorded and reported by the IWRS.

If an investigator, site personnel performing assessments, or participant is unblinded, the participant must be discontinued from the study. In cases where there are ethical reasons to have the participant remain in the study the investigator must obtain specific approval from a Lilly clinical research physician (CRP) for the participant to continue in the study.

In case of an emergency, the investigator has the sole responsibility for determining if unblinding of a participant's treatment assignment is warranted for medical management of the event. The participant's safety must always be the first consideration in making such a determination. If a participant's treatment assignment is unblinded, Lilly must be notified immediately. If the investigator decides that unblinding is warranted, it is the responsibility of the investigator to promptly document the decision and rationale and notify Lilly as soon as possible.

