For the primary and key secondary efficacy endpoint analyses subject to type 1 error rate control, data for participants with missing values at the 72-week visit will be imputed based on the method described in Section 4.3.2.3. Otherwise, missing values will not be explicitly imputed except for the parameters with only 1 postbaseline measure during the analysis period per the schedule of activity, where the last-observation-carried-forward (LOCF) approach will be applied to impute the endpoint when ED measure is available.

End of study participation for a participant will be the earliest of date of death, date of withdrawal from further participation in the study, or date of safety follow-up visit (Visit 801). For participants considered to be lost to follow-up, end of study participation will be the date of lost to follow-up reported by the investigator. Participant data included in the database after the last date of study participation will be excluded from statistical analysis.

Statistical summaries and results of statistical analyses will be displayed in the following order: Placebo, tirzepatide MTD.

Not all analyses described in this SAP will necessarily be included in the clinical study reports (CSRs). Any analysis described in this SAP and not provided in the CSR would be available upon request. Not all displays will necessarily be created as a “static” display. Some may be incorporated into interactive display tools instead of or in addition to a static display.

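### Protocol 6.3 and one Protocol 7.2 bullet end study participation, not only study drug, so some Week 72 weights needed for the treatment-regimen estimand may not be collected

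*Protocol*

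**What the plan says.** **Rules that end participation.** Protocol 6.3: "If an investigator, site personnel performing assessments, or participant is unblinded, the participant must be discontinued from the study". The exception is for ethical reasons, and then "the investigator must obtain specific approval from a Lilly clinical research physician (CRP) for the participant to continue in the study". Protocol 7.2 lists circumstances in which a participant may leave the study. One bullet covers a participant who needs a drug, device or surgical treatment known to work for the indication, and it ends: "discontinuation from the study occurs prior to introduction of the new treatment". The closing paragraph of 7.2 says that someone who discontinues from the study leaves both the intervention and the study at that point.

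**Rules that keep people in.** Protocol 7.1 says that when study drug is stopped for good, "the participant will remain in the study to be evaluated for any trial endpoint at the end of the study", and later: "Participants who stop the study drug permanently should perform an ED visit and continue to attend all scheduled study visits". The same section lists starting an open-label GLP-1R agonist among the reasons to stop the intervention. Visit 99 (Protocol 1.3 notes, Protocol 4.1.1.2.3, SAP 1.2) obtains a Week 72 weight from people who stop treatment early and decline their remaining visits. Protocol 7.2 opens by asking sites to make every attempt at retention. It also says that people who agree to supply endpoint information at the end are not treated as having discontinued.

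**Analysis.** SAP 1.1.2.1 applies a treatment-policy strategy to the treatment-regimen estimand. SAP 4.3.2.3 imputes missing Week 72 weights from retrieved dropouts in the same arm. SAP 4.1 adds: "End of study participation for a participant will be the earliest of date of death, date of withdrawal from further participation in the study", or the date of Visit 801, and "Participant data included in the database after the last date of study participation will be excluded from statistical analysis".

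**The concern.** A treatment-policy estimand needs the Week 72 weight of everyone in the analysis population, including people who stop study drug and move to another obesity treatment. A rule that ends participation at that moment works against collecting it. The unblinding rule can do the same for a different reason.

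Sites also receive two instructions for one event. A participant who starts an open-label GLP-1R agonist stops drug and is followed under 7.1, but exits the study under the 7.2 bullet.

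The lost weights are unlikely to be a random subset. People who leave before starting another effective treatment will be under-represented among the retrieved dropouts who serve as donors. If more placebo than tirzepatide participants leave this way, the placebo mean is imputed somewhat too heavy and the treatment difference is slightly overstated. If exits are balanced, with similar effects in the two arms, the cost is only avoidable missing data. The sensitivity analyses in SAP 4.3.2.4 change the imputation method but cannot recover the weights.

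**Working it through.** **1. The texts side by side**

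| Event after randomization | Rule | Week 72 weight |
|---|---|---|
| Stops study drug | 7.1: stays in the study | Visit 28 or Visit 99 |
| Starts open-label GLP-1R agonist | 7.1: stop drug, stay; 7.2 bullet: leave the study | Depends on the section followed |
| Needs other effective obesity treatment | 7.2 bullet: leave the study | No route stated in the bullet |
| Unblinded | 6.3: leave, unless the sponsor physician approves | No route stated in 6.3 |

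Visit 99 is described for people who decline visits. That does not plainly describe someone removed by rule.

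**2. The plan's own power figure** (Protocol 9.2, SAP 5)

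Inputs: 300 per arm, 25% dropout, difference 12 points, SD 10, responders 20% versus 46%, two-sided 0.05.

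- Evaluable per arm: 300 × (1 − 0.25) = 225.
- SE of the difference: 10 × √(2/225) = 0.943. Then 12 / 0.943 = 12.7, so power is about 100%.
- Responders: pooled rate 0.33. Null SE = √(2 × 0.33 × 0.67 / 225) = 0.0443. Alternative SE = √((0.20 × 0.80 + 0.46 × 0.54) / 225) = 0.0426. Then z = (0.26 − 1.96 × 0.0443) / 0.0426 = 4.06, so power is 99.998%.

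Both agree with the stated figure of more than 90%.

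**3. Power after extra losses**

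The documents give no exit rate, so the range is assumed. Losing a further 1% to 10% of weights leaves 222 to 195 per arm. Power stays at about 100% for the mean and runs from 99.997% to 99.99% for responders.

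**4. Shift in the estimate from other obesity treatment**

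Shift = d × e. Here d is the share of placebo leaving with no weight minus the same share on tirzepatide. The term e is the unobserved extra weight loss, taken as similar in both arms. For drugs, Protocol 2.2 gives a placebo-adjusted effect of 3% to 7%.

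- d = 1% (3 of 300): 0.01 × 3 = 0.03 and 0.01 × 7 = 0.07 points.
- Relative to 12 points: 0.25% to 0.58%. Relative to the SE of 0.943: 0.03 to 0.07 SE.
- Net share needed for a 1-point shift: 1/7 = 14.3% (43 of 300) to 1/3 = 33.3% (100 of 300).
- Balanced exits with similar effect: 0.

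For drug starters these values lean high. Someone who starts part-way gains less, some leavers will still give a weight, and the donors can include GLP-1R agonist starters kept under 7.1. The documents give no device or surgical effect. If 10 points is assumed, the shift is 0.01 × 10 = 0.10 points per net 1%, or 0.83% of 12.

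**5. Would it change the conclusion?**

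With a full 1-point shift, 11 / 0.943 = 11.7, so power for the mean stays above 99.9%. For responders, suppose a net 10% of placebo leaves and every non-responder among them would have responded. The placebo rate becomes 0.20 + 0.10 × 0.80 = 28%, and power at 225 per arm is 97.9%, still above 90%.

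**6. Unblinding**

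Nothing in the documents gives a frequency or a direction, so no bias figure can be derived. Each such exit puts one primary weight at risk.

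**The case against.** The strongest reply is that the protocol already handles this. Section 7.2 asks for every attempt at retention, its bullet sits in a permissive list, and people who agree to give endpoint information are not counted as having left. Section 6.3 restricts emergency unblinding to cases where the participant's well-being requires it, and it allows staying with approval. For GLP-1R agonists, 7.1 stops only the drug. The disposition figure in 7.2.1, which the Visit 99 text cites, was not available in the text we read and may route these people to Visit 99. The numerical effect is very small.

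Most of this stands, and it limits the point to weights that may not be collected. It does not remove it. The wording of 6.3 is mandatory, with a case-by-case exception. The 7.2 bullet states what happens, not what may happen. The sentence about endpoint information works only if the participant is asked, and nothing in the readable text tells sites to ask someone removed by rule.

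A reader might go further and infer that SAP 4.1 makes a Week 72 weight unusable even when it is obtained after such an exit. The documents do not support that as a firm reading. Under the 7.2 sentence, a participant who supplies the weight has not discontinued. There is then no withdrawal date to trigger the exclusion. The closing paragraph of 7.2 pulls the other way, so the matter is ambiguous.

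**Conclusion.** The point holds in a limited form. Two protocol rules end participation where ending study drug would be enough, against the protocol's own retention rules and the treatment-policy estimand. Some Week 72 weights may not be collected as a result.

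Only the treatment-regimen estimand is affected, because the efficacy estimand already leaves out data after drug discontinuation (SAP 1.1.2.1). The size is about 0.03 to 0.07 points per net 1% of placebo leaving for another drug. This rests on the 3% to 7% effect in Protocol 2.2 and on exit rates that the documents do not give. The direction favours tirzepatide if placebo participants leave more often, and it is unknown for unblinding.

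A reader might infer a threat to the superiority conclusion. The arithmetic does not support that: even a 1-point shift leaves the mean comparison at z = 11.7. This is a cheap improvement of the lowest severity. Confidence is medium, because the 7.2.1 figure could not be checked.

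**What to change.** Amend Protocol 6.3 and the 7.2 bullet so that a participant who is unblinded, or who starts another effective obesity treatment, stops study drug if required but stays in the study for data collection. State that Visit 99, with its Week 72 weight, applies to these participants unless they withdraw consent. Leave the pregnancy withdrawal rule in 7.2 as it is. Extending Visit 99 to every randomized participant would collide with that rule.

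Protocol 4.1.1.3 places Visit 801 four weeks after Visit 28 or Visit 99, or "4 weeks after the ED visit for randomized participants who decline to return for Visit 99". Once these participants are routed to Visit 99, participation runs past the Week 72 weight. The SAP 4.1 cut-off then cannot remove it, and the SAP needs no change. The amendment concerns data collection only, not whether or when any treatment is given.

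The cost is about two sentences of protocol text with the usual ethics and authority approvals, and a few more attendances at a visit that already exists.
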